### 6.3.2 Early Clinical Response Plus Improvement in Vital Signs

Subjects will be programmatically defined as a **responder** if the following 5 criteria are met:

- Alive;
- Improvement in at least 2 of the 3 or 4 cardinal symptoms of CABP the subject presented with at baseline. Improvement is defined as a decrease by at least 1 level of severity;
- No worsening of any of the 4 cardinal symptoms of CABP. Worsening is defined as an increase by at least 1 level of severity for any symptom;
- Improvement in all vital signs (ie, body temperature, blood pressure, heart rate, respiratory rate) that were abnormal at baseline. Improvement is defined as returning to normal. If a vital sign was normal at baseline (ie, not abnormal as per the definitions below), it cannot have worsened. Abnormal vital signs are defined as:
  - Fever: defined as body temperature >38.0°C (100.4°F) measured orally, >38.5°C (101.3°F) measured tympanically, >39.0°C (102.2°F) measured rectally, or >37.5°C (99.5°F) by axillary measurement
  - Hypothermia: defined as body temperature <35.0°C (95.0°F) measured orally, <35.5°C (95.9°F) measured tympanically, <36.0°C (96.8°F) measured rectally, or <34.5°C (94.1°F) by axillary measurement
  - Hypotension: defined as systolic blood pressure <90 mmHg
  - Tachycardia: defined as heart rate >100 beats/min
  - Tachypnea: defined as respiratory rate >20 breaths/min
- Did not receive a concomitant antibiotic for the treatment of CABP up through the assessment of the cardinal symptoms of CABP.

Subjects will be programmatically defined as a **non-responder** if any of the following are met:

- Did not show an improvement in at least 2 of the 3 or 4 cardinal symptoms of CABP the subject presented with at baseline. Improvement is defined as a decrease by at least 1 level of severity; or
- Worsening of any of the 4 cardinal symptoms of CABP. Worsening is defined as an increase by at least 1 level of severity for any symptom; or
- Did not show an improvement in all vital signs that was abnormal at baseline. Improvement is defined as the following:

- Body temperature 35.0 to 38.0°C (95.0 to 100.4°F) measured orally, 35.5 to 38.5°C (95.9 to 101.3°F), measured tympanically, or 36.0 to 39.0°C (96.8 to 102.2°F) measured rectally or 34.5 to 37.5°C (94.1 to 99.5°F) by axillary measurement
- Systolic blood pressure  $\geq 90$  mmHg
- Heart rate  $>50$  to  $\leq 100$  beats/min
- Respiratory rate  $\leq 20$  breaths/min; or
- Received a concomitant antibiotic for the treatment of CABP up through the assessment of the cardinal symptoms of CABP, or if no assessment was completed, up to 120 hours after the first dose of study drug (or randomization if the subject did not receive study drug); or
- Died from any cause up through the assessment of the cardinal symptoms of CABP, or if no assessment was completed, up through Study Day 5.

Section 6.1 describes rules for determining the outcome if more than 1 assessment of symptoms is obtained in the  $96 \pm 24$  hour window or if no assessment of symptoms is obtained in the  $96 \pm 24$  hour window. Subjects with missing data such that a response cannot be determined will be considered to have an indeterminate response. Subjects who did not have at least 2 symptoms of CABP at baseline or who did not have an assessment of vital signs at baseline will also be considered to have an indeterminate response. Since the analysis of ECR plus improvement in vital signs is based on the ITT Analysis Set, subjects with an indeterminate response are essentially considered non-responders. For the ITT Analysis Set, the percentage of ITT subjects determined to be responders for ECR plus improvement in vital signs is defined using the following formula (where the denominator is comprised of the total number of subjects in the ITT Analysis Set):

$$\frac{\text{Number of subjects who are a responder}}{(\text{Number of subjects who are a responder} + \text{Number of subjects who are a non-responder} + \text{Number of indeterminate subjects})} \times 100\%$$

#### 6.4 Other Microbiological Outcomes

Superinfections are defined as new pathogens (ie, pathogen(s) not present at baseline) identified in post-baseline cultures through the TOC Visit with persistent signs and symptoms of CABP (ie, IACR of failure at the TOC Visit), such that additional antibacterial therapy is necessary for current episode of CABP.

Colonization is defined as new pathogens (ie, pathogen(s) not present at baseline) identified in at least 2 post-baseline cultures through the TOC Visit but signs and symptoms of CABP have resolved (ie, IACR of success at the TOC Visit), such that no additional antibacterial therapy is necessary for the current episode of CABP.

Development of decreasing susceptibility is defined as a  $\geq 4x$  increase from baseline in MIC to the study drug received or a  $\geq 6$  mm decrease from baseline in disk inhibition zone diameter to the study drug received for a baseline pathogen subsequently isolated from culture of a post-baseline blood or respiratory sample (ie, for a post-baseline pathogen).

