#### • Colonization:

New respiratory (i.e., from sputum, pleural fluid or BAL specimen) pathogen(s), (i.e., pathogen(s) not present at baseline) identified in at least 2 post-baseline cultures

through the TOC Visit but signs and symptoms of CABP have resolved, (i.e., IACR of Success at the TOC Visit, such that no additional antibacterial therapy is necessary for the current episode of CABP).

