#### • Development of Decreasing Susceptibility:

- Increase in MIC ( $\geq 4x$ ) or 6 mm decrease from baseline in disk inhibition zone diameter to the study drug received for a pathogen isolated at baseline and subsequently isolated from a blood or lower respiratory tract specimen.

ECR plus improvement in vital signs (i.e., body temperature, blood pressure, heart rate, respiratory rate), if abnormal at Baseline will be evaluated in the ITT Analysis set. If vital signs are normal at Baseline (i.e., not abnormal as per the definitions below), none can have worsened.

Abnormal vital signs are defined as:

- Fever: [defined as body temperature > 38.0 °C (100.4 °F) measured orally, > 38.5 °C (101.3 °F) measured tympanically, or > 39.0 °C (102.2 °F) measured rectally]
- Hypothermia: [defined as body temperature < 35.0 °C (95.0 °F) measured orally, < 35.5 °C (95.9 °F) measured tympanically, or < 36.0 °C (96.8 °F) measured rectally]
- Hypotension: defined as systolic blood pressure < 90 mmHg
- Tachycardia: defined as heart rate > 100 bpm
- Tachypnea: defined as respiratory rate > 20 breaths/min

Exploratory evaluation of a variety of health utilization variables (e.g., length of hospital stay, duration of antibiotic therapy, discharge status, discharge destination) as well as a PRO instrument will be performed. Details for this exploratory analysis will be presented in a separate SAP and results will be presented in a stand-alone clinical study report.

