#### **4.0 PATHOGEN IDENTIFICATION**

All microbiology data will be reviewed by the Sponsor for pathogen identification. A pathogen is defined as bacteria implicated as causative in a subject's CABP and will be determined separately for each subject. Baseline pathogens and post-baseline pathogens will be identified.

Additional details regarding the pathogen review process and determination are included in the Evaluability Review Plan.

Baseline for microbiologic specimens is defined as the 24-hour period prior to the administration of the first dose of study drug and the 24 hours after the first dose of study drug. A pathogen identified from a respiratory (pleural fluid, bronchoalveolar lavage (BAL), sputum), blood for culture, urine, nasopharyngeal or oropharyngeal specimen collected at baseline is considered a baseline pathogen. An atypical pathogen identified by serology is considered a baseline pathogen if the baseline sample is collected in the 24-hour period prior to the administration of the first dose of study drug or the 24 hours after the first dose of study. A Gram stain from a specimen collected at baseline is considered a baseline Gram stain.

If more than 1 specimen is taken during the baseline period, all specimens will be reviewed for pathogen identification. If the same pathogen (based on genus and species) is identified from more than 1 specimen, the pathogen with the highest minimum inhibitory concentration (MIC) to study drug received will be considered the baseline pathogen. If the pathogens have the same MIC to study drug received, the one with the highest accession number will be considered the baseline pathogen.

Post-baseline is defined as the period starting 24 hours after the first dose of study drug. A pathogen identified from a specimen collected post-baseline is considered a post-baseline pathogen. Only pathogens identified by culture of the sputum, BAL, pleural fluid or blood are considered post-baseline pathogens.

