**Streptococcus pneumoniae**

- Positive BAL, pleural fluid or blood culture; or
- Positive sputum culture in the presence of a Gram stain with >25 PMNs/LPF and <10 SECs/LPF (**NOTE:**  $\geq 10$  PMNs/LPF and <10 SECs/LPF in the expanded Microbiological ITT (emicroITT) Analysis Set); or
- Positive urinary antigen test; or
- Positive real-time quantitative Polymerase chain reaction (RQ-PCR) of nasopharyngeal swab or sputum (see [Table 1](#) for cutoff values); or
- Positive nasopharyngeal specimen culture

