A by-subject listing of subjects in the ITT Analysis Set with a superinfection or colonization will be provided. The listing will include subject ID, treatment group, baseline and post-baseline pathogen genus and species, study day of post-baseline pathogen, and whether the emergent pathogen is a superinfection or a colonization.

A by-subject listing of subjects in the ITT Analysis Set showing at least 1 pathogen with decreasing susceptibility will be presented in a listing providing the subject ID, treatment group, collection date/time and study day, type of specimen, pathogen (baseline and post-baseline), MIC values, disk diffusion zone diameters, and susceptibility to study drug received.

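### SAP 6.4 narrows decreasing susceptibility and drops the respiratory-source requirement from superinfection and colonization, and SAP 9.0 declares none of these departures from protocol 9.4.5

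*SAP*

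**What the plan says.** **Decreasing susceptibility.** Protocol 9.4.5 requires an MIC rise of at least 4-fold, or a 6 mm fall in zone diameter, "for a pathogen isolated at baseline and subsequently isolated from a blood or lower respiratory tract specimen". It sets no further test on the later isolate. SAP 6.4 uses the same MIC threshold and writes the zone change as at least 6 mm, but applies them "for a baseline pathogen subsequently isolated from culture of a post-baseline blood or respiratory sample (ie, for a post-baseline pathogen".

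**Post-baseline pathogen.** SAP 4.0 states: "Only pathogens identified by culture of the sputum, BAL, pleural fluid or blood are considered post-baseline pathogens". SAP 6.2.3 says post-baseline organisms count as pathogens according to the Section 4.0 criteria. For sputum, the criterion in SAP 4.1 is "Positive sputum culture in the presence of a Gram stain with >25 PMNs/LPF and <10 SECs/LPF". It is the same for *S. pneumoniae*, *H. influenzae*, *S. aureus* and *M. catarrhalis*, and SAP 4.2 repeats it for *M. pneumoniae*.

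**Superinfection and colonization.** In protocol 9.4.5 both definitions open with "New respiratory (i.e., from sputum, pleural fluid or BAL specimen) pathogen(s". SAP 6.4 has no such restriction: "Colonization is defined as new pathogens (ie, pathogen(s) not present at baseline) identified in at least 2 post-baseline cultures through the TOC Visit". Its superinfection definition omits the source in the same way.

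**Listings and declared changes.** The superinfection/colonization listing in SAP 8.5.4.2 gives subject, treatment, organisms, study day and "whether the emergent pathogen is a superinfection or a colonization", but not the specimen. The decreasing-susceptibility listing beside it does give specimen type. SAP 9.0 lists added analysis sets and added analyses only.

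**The concern.** A Gram-stain threshold helps to judge whether an organism caused the pneumonia. Decreasing susceptibility asks something else: whether an organism already accepted as the baseline pathogen came back with a higher MIC or a smaller zone. Putting the causation test on the second isolate removes events that the protocol would count and can add none. This outcome is the only one in SAP 6.4 that addresses treatment-emergent loss of susceptibility, and the sponsor does report on it: protocol 1.5.2 says none was seen for lefamulin in Phase 2. A similar statement from this trial would rest on a narrower rule than the protocol's, and the reader would not be told.

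With the source requirement gone, a repeated new bloodstream isolate can carry a label that suggests harmless airway carriage, and the listing has no column from which a reader could see otherwise.

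**Working it through.** No arithmetic applies, and the documents give no counts. The check sets the definitions side by side and follows two cases through them.

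| Element | Protocol 9.4.5 | SAP 6.4 | Effect |
|---|---|---|---|
| Decreasing susceptibility: status of later isolate | Any re-isolate from blood or lower respiratory tract | Must be a post-baseline pathogen | Narrower |
| Decreasing susceptibility: zone change | 6 mm | At least 6 mm | Clarification |
| Decreasing susceptibility: specimen | Blood or lower respiratory tract | Blood or respiratory | None: SAP 4.0 takes respiratory to mean pleural fluid, BAL or sputum |
| Superinfection: source | Sputum, pleural fluid or BAL | Not restricted | Blood admitted through SAP 4.0 |
| Colonization: source | Sputum, pleural fluid or BAL | Not restricted | Blood admitted through SAP 4.0 |

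**Case 1.** A baseline *S. pneumoniae* grows again more than 24 hours after the first dose, with a 4-fold higher MIC, from sputum showing 10-25 PMNs and fewer than 10 SECs per LPF.
- Protocol: same organism, lower respiratory specimen, MIC criterion met. It counts.
- SAP: the sputum fails the criterion of more than 25 PMNs, so under SAP 4.1 and 6.2.3 the isolate is not a post-baseline pathogen. It does not count.
- Table 5 confirms that the SAP foresees this situation. It provides for the baseline organism regrowing without meeting the pathogen definition, and scores that as eradication. If no other culture shows persistence, the isolate appears neither as persistence nor in the decreasing-susceptibility listing. The eradication score comes from Table 5 and is not changed by SAP 6.4.

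The reach of Case 1 is limited. Blood, BAL and pleural fluid cultures need no Gram stain, and a sputum culture of *L. pneumophila* counts whatever the stain shows (SAP 4.2). Only sputum isolates that fail the criterion are lost.

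**Case 2.** A new organism, judged to be a pathogen, grows in two post-baseline blood cultures by TOC, and the IACR at TOC is success.
- Protocol: not respiratory, so not colonization.
- SAP: all conditions for colonization are met.
- With only one positive culture it would not be colonization. With an IACR of failure and further treatment needed it would be superinfection, which under the protocol also required a respiratory source.

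**Declaration.** SAP 9.0 mentions none of the three definitions.

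**The case against.** **The parenthesis may only restate the clause before it.** SAP 4.1 says that organisms meeting its criteria are always pathogens, which taken literally is a sufficient condition, and the Gram-stain exclusion is reached through text written for microbiological response. This shows that the strict reading is not certain. It remains the natural one, because the SAP uses pathogen as a defined term, 6.2.3 ties post-baseline organisms to it, and Table 5 separates regrowth of the same organism from a pathogen. If no restriction was meant, deleting the parenthesis loses nothing.

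**Specimen adequacy is relevant.** A re-isolate from poor sputum may be an upper-airway strain of the same species, and protocol 6.15.1 uses the same adequacy standard at Screening. This stands in part. The protocol's definition is silent on Gram stain, so adequacy is better shown as a flag than used as an exclusion.

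**The protocol is itself incomplete on blood.** The sentence in 9.4.5 that introduces these categories mentions blood as well as respiratory cultures, yet neither superinfection nor colonization then admits a blood isolate. The SAP may have meant to fill that gap. This stands as an explanation, but the SAP does not say so.

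**Stronger readings that a reader might infer, and that the documents do not support:**
- *That a bacteremia would be hidden.* SAP 7.5 puts all clinical data in by-subject listings, protocol 6.15.4 records local culture results in the eCRF, and a new bacteremia may also be reported as an adverse event.
- *That the losses fall mainly in improving subjects.* After Screening, sputum is taken only when clinically indicated, and repeat cultures are sought on discontinuation for clinical failure (protocol 6.15.1). Nothing in the documents describes how sputum PMNs change with recovery.
- *That this is the trial's main resistance outcome.* No stated objective mentions it. The protocol places it under Other Variables, and the SAP presents it only as a listing.

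**Conclusion.** The inconsistency is real and undeclared, and its importance is minor. Relative to the protocol, the SAP's decreasing-susceptibility listing can only under-count, and only through sputum isolates that fail the Gram-stain criterion. Superinfection and colonization both admit blood isolates that the protocol excluded. The colonization case needs two positive cultures, clinical success and a judgement that the organism is a pathogen, so it is likely to be rare.

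The number of isolates involved cannot be derived from the documents and is expected to be small. No primary, secondary or non-inferiority result is affected, since these outcomes have no rate, interval or test. The conclusion on decreasing susceptibility assumes that post-baseline pathogen in SAP 6.4 carries the meaning given in SAP 4.0 to 4.2 and 6.2.3. The conclusion on source rests directly on the wording of the two documents.

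**What to change.** 1. In SAP 6.4, delete the parenthesis that limits decreasing susceptibility to a post-baseline pathogen, so that the protocol definition applies. List every re-isolate of a baseline pathogen from blood or a lower respiratory specimen that meets the MIC or zone criterion, and flag those from sputum that fails the Gram-stain criterion.
2. In SAP 6.4, restore the respiratory source (sputum, pleural fluid or BAL) in both superinfection and colonization, and list new blood isolates separately.
3. In SAP 8.5.4.2, add specimen type to the superinfection/colonization listing.
4. Declare any difference that is kept in SAP 9.0, with the reason.

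The cost is SAP wording and changes to two listing programs, using data already collected. The downside is a few more listed isolates, some of which may be upper-airway contaminants; the flag identifies them.

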## 6.5 Pharmacokinetic Outcomes

Measured plasma concentrations of BC-3781 and BC-8041 will be summarized for subjects in the lefamulin group.

## 6.6 Safety Outcomes

Safety will be assessed by analysis of AEs and changes in laboratory parameters (chemistry and hematology), electrocardiogram (ECG) parameters, and vital signs. Laboratory abnormalities are not considered AEs unless they are associated with clinical signs and symptoms or require medical intervention. Clinically significant abnormal clinical laboratory findings or other abnormal assessments that are associated with the disease being studied, unless judged by the Investigator as more severe than expected for the subject's condition, or that are present or detected at the start of the study and do not worsen, will not be reported as AEs or SAEs.

## 6.7 Additional Exploratory Outcomes

Exploratory evaluation of a variety of health utilization variables (eg, length of hospital stay, discharge status and discharge destination) and a patient-reported outcome instrument (SF-12) will be performed. Details of this exploratory analysis will be presented in a separate SAP and results will be presented in a separate report.

## 7.0 STATISTICAL METHODS

### 7.1 Sample Size

A total of 738 subjects will be randomized in a ratio of 1:1 (lefamulin:moxifloxacin) resulting in 369 subjects in the lefamulin arm and 369 in the moxifloxacin arm in this study. The total number of subjects included in this study is sufficient to achieve the primary and secondary study objectives based on statistical considerations.

Retrospective analyses of clinical study data for patients with CABP of varying severity as well as 2 recent clinical trials in CABP indicate the point estimates for an ECR responder at Days 3-5 range from 72% to 81% (FDA, 2011; Barrera et al., 2016; Cempra, 2015; Oldach et al., 2015). Thus, it is reasonable to assume that in a prospective study of subjects with CABP, the proportion of subjects who are responders for ECR at  $96 \pm 24$  hours post first dose of study drug will be approximately 79%.

The primary efficacy analysis variables used for NI analyses for the Marketing Authorization Application (MAA) to the EMA will be the proportion of subjects with an IACR of Success at TOC in the mITT and CE-TOC Analysis Sets. In recent clinical studies, IACR success rates at the TOC Visit in the CE Analysis Set ranged from 77% to 93% (Cempra, 2015) and in the ITT

Analysis Set ranged from 85% to 89% depending on the antibiotics under study and the severity of the CABP. Based on these data, an 85% IACR success rate in the CE-TOC Analysis Set was chosen for determination of the sample size. The success rate is expected to be about 5% lower in the mITT Analysis Set. It is expected that <1% of subjects will be excluded from the mITT Analysis Set and thus, the sample size determination assumes the same number of subjects in the ITT and mITT Analysis Sets.

Utilizing an anticipated ECR responder rate of 79% in the ITT Analysis Set, a 1:1 randomization ratio, a one-sided alpha of 0.025, and a continuity corrected Z-test with unpooled variance, a sample size of 738 subjects (369 subjects in the lefamulin group and 369 in the moxifloxacin group) provides 90% power to establish the NI of lefamulin to moxifloxacin for ECR using a NI margin of 10.0%. Assuming an IACR success of 80% and 85% in the mITT and CE-TOC Analysis Sets, respectively, and a clinical evaluability rate of 80%, there is 91% power for demonstration of NI for IACR at the TOC Visit using a 10% NI margin.

The calculated power in each analysis set for the primary and secondary outcomes is provided in [Table 7](#).

**Table 7. Power Calculations for the Primary and Secondary Efficacy Outcomes**

Analysis Set	Primary Outcome (FDA) (ECR 96 ± 24 hours After the First Dose of Study Drug)	Secondary Outcome (Investigator’s Assessment of Clinical Response at TOC- Primary for EMA)	
	ITT	mITT	CE-TOC
NI Margin	10%	10%	10%
N	738 (369:369)	738	590
Outcome Rate	79%	80%	85%
Evaluability Rate	NA	NA	80%
Power	90%	91 %	91%

CE = clinically evaluable; ITT = intent to treat; mITT = modified ITT; TOC = test of cure

## 7.2 Visit Windows

### 7.2.1 Baseline

Unless otherwise stated below, baseline is defined as the last measurement prior to the first dose of study drug.

- For microbiological pathogen determination, baseline is defined as the 24-hour period prior to the administration of the first dose of study drug and the 24 hours after the first dose of study drug. A pathogen identified from a respiratory (pleural fluid, bronchoalveolar lavage (BAL), sputum), blood for culture, urine, nasopharyngeal or oropharyngeal specimen collected at baseline is considered a baseline pathogen. An atypical pathogen identified by serology is considered a baseline pathogen if the baseline

sample is collected in the 24-hour period prior to or the 24 hours after the administration of the first dose of study drug.

- For vital signs, baseline is defined as the Screening assessment (since time of assessment is not captured) as long as the date of collection is on or before the date of first dose of study drug.
- For ECGs, baseline is defined as the mean of the triplicates (or duplicate or single, if a triplicate is not obtained) from the last assessment prior to the first dose of study drug, including scheduled and unscheduled visits.
- If no study drug is received, baseline is defined as the measurement taken at the Screening Visit (ie, prior to the randomization date/time)

Study Day 1 is defined as the first calendar day of study drug administration (or the date of randomization if no study drug was received). The calendar day prior to the first dose of study drug (or randomization day if no study drug is received) is Study Day -1; there is no Study Day 0.

For all clinical assessments and procedures performed prior to the date of the first study drug administration, study day will be calculated as the date of the assessment minus the date of the first dose of study drug. For all clinical assessments and procedures performed on or after the date of the first dose of study drug, study day will be calculated as the date of the assessment minus the date of the first dose of study drug, plus 1.

